**Figure 4 Follow-up: Variable B-Cell Monitoring Period**

During the Follow-up Period, patients will be formally assessed at clinical visits every 24 weeks and by telephone contacts every 8 weeks. If further B-cell monitoring is required and the patient is not receiving any other B-cell targeted therapy, assessments will take place at clinical visits every 24 weeks and by telephone contacts every 8 weeks until the B-cells are repleted. See [Appendix 2](#) for further details.

After initiation of study drug, all adverse events will be reported until 96 weeks after the end of the Treatment Period but may be extended in patients whose B-cells take longer to replete.

Related SAEs must be collected and reported regardless of the time elapsed from the last study drug administration, even if the study has been closed.

For patients withdrawing from treatment early, every effort should be made to complete the Follow-up Period and all related assessments regardless of whether or not they receive alternative treatment for MS.

A dedicated (scheduled or unscheduled) follow-up clinic visit directly prior to the start of an alternative MS treatment is required in order to assess the patient's clinical status and safety parameters (assessments to be performed as per [Appendix 2](#), Schedule of Assessments: Follow-up including further B-cell monitoring period).

Patients who receive alternative MS therapies that may decrease B-cell levels will only be followed up for 96 weeks; they will not be entered into the prolonged B-cell Monitoring period thereafter.

A structured telephone interview will be conducted by site personnel every 8 weeks between the study visits during the treatment period and follow-up to identify and collect information on any changes in the patient's health status that warrant an unscheduled

visit (including new or worsening neurological symptoms) and possible events or infections.

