#### Exclusions Related to Medications\*

- Receipt of a live vaccine or attenuated live vaccine within 6 weeks prior to the baseline visit. In rare cases when patient requires vaccination with a live vaccine, the screening period may be extended but cannot exceed 8 weeks
- Treatment with any investigational agent within 24 weeks of screening (Visit 1) or five half-lives of the investigational drug (whichever is longer) or treatment with any experimental procedures for MS (e.g., treatment for chronic cerebrospinal venous insufficiency)
- Contraindications to or intolerance of oral or IV corticosteroids, according to the country label, including:
  - a) Psychosis not yet controlled by a treatment;
  - b) Hypersensitivity to any of the constituents
- Previous treatment with B-cell targeted therapies (i.e., rituximab, ocrelizumab, atacicept, belimumab, or ofatumumab)
- Systemic corticosteroid therapy within 4 weeks prior to screening
- Any previous treatment with alemtuzumab (Campath/Mabcampath/Lemtrada), cladribine, mitoxantrone, daclizumab, laquinimod, total body irradiation, or bone marrow transplantation.
- Treatment with cyclophosphamide, azathioprine, mycophenolate mofetil, cyclosporine or methotrexate
- Previous treatment with natalizumab unless natalizumab was discontinued because of persistent anti-natalizumab antibodies
- Treatment with IV immunoglobulin (Ig) within 12 weeks prior to baseline

- Any previous treatment with an investigational MS DMT not yet approved at time of screening.
- History of recurrent aspiration pneumonia requiring antibiotic therapy
- Patients previously treated with teriflunomide, unless an accelerated elimination procedure is implemented before screening visit

Accelerated elimination procedure after stopping treatment with teriflunomide:

- cholestyramine 8g is administered 3 times daily for a period of 11 days, or cholestyramine 4g three times a day can be used, if cholestyramine 8g three times a day is not well tolerated,
- alternatively, 50g of activated powdered charcoal is administered every 12 hours for a period of 11 days

In cases where no pregnancy is expected teriflunomide plasma concentrations of 0.03-0.04 mg/ml are accepted to include the patient in study.

- Previous treatment with fingolimod or dimethyl fumarate if at baseline the lymphocyte count is below lower limit of normal (LLN). The provisions for stopping therapy as described in the respective SmPCs should be followed.

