## **3. STUDY DESIGN**

### **3.1 DESCRIPTION OF THE STUDY**

This study is a prospective, multicenter, open-label, efficacy and safety study in patients with RRMS who have had a suboptimal response to an adequate course of a DMT. An adequate course of prior DMT is defined as a stable dose of the same DMT administered for at least 6 months. The first dose of ocrelizumab will be administered as an initial dose of two 300-mg infusions (600 mg total) in 250 mL 0.9% sodium chloride

each separated by 14 days (i.e., Days 1 and 15) followed by one 600-mg infusion in 500 mL 0.9% sodium chloride every 24 weeks for the remainder of the study duration.

This study will enroll 750 patients. Patients will be assessed for efficacy and safety every 24 weeks as described in the Schedule of Assessments presented in [Appendix 1](#).

The study will consist of the following periods:

- Screening period: Up to 4 weeks
- Treatment period: Open-label treatment period of 96 weeks (last dose administered at Week 72)
- A follow-up period of at least 2 years, which is independent of the DMT administered

Follow-up Period: Patients who discontinue treatment early will be followed up for at least 96 weeks after the Early Treatment Discontinuation Visit. Patients who complete the 96 weeks Treatment Period and, in agreement with their treating neurologist, decide not to continue in a separate long-term extension (LTE) study, will be followed up for at least 96 weeks after the end of the Treatment Period. Patients who decide to leave the study and switch to commercially marketed Ocrelizumab, either after completion of the 96 weeks Treatment Period or after early discontinuation of the 96 weeks Treatment Period, will not enter the safety Follow-up Period.

[figure not shown]
Patients whose B-cells have not been repleted after 96 weeks of Follow-up Period will continue with visits every 24 weeks, and telephone contacts every 8 weeks, until B-cell repletion (Prolonged B-cell monitoring). If the patients are receiving other B-cell targeted therapies, then the Follow-up Period will be stopped at 96 weeks regardless of their B-cell count.

A structured telephone interview will be conducted by site personnel every 8 weeks between the study visits during the treatment period and follow-up to identify and collect information on any changes in the patient's health status that warrant an unscheduled visit (including new or worsening neurological symptoms) and possible events or infections.

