**Figure 3 Overview of End of Treatment Period**

### **3.1.4 Follow-up Period**

[figure not shown]
Patients who discontinue treatment early will be followed up for at least 96 weeks after the Early Treatment Discontinuation Visit. Patients who complete the 96 weeks Treatment Period and, in agreement with their treating neurologist, decide not to continue in a separate LTE study, will be followed up for at least 96 weeks after the end of the Treatment Period.

Patients who decide to leave the study and switch to commercially marketed Ocrelizumab, either after completion of the 96 weeks Treatment Period or after early discontinuation of the 96 weeks Treatment Period, will not enter the safety Follow-up Period.

Any patient whose peripheral blood B-cell count remains depleted after this period will continue to be monitored at 24-week intervals until the B-cell count has returned to the baseline value or to lower limit of normal (LLN) range, whichever is lower.

[Figure 4](#) provides an overview of the Follow-up Period, which is the variable B-cell monitoring period. A schedule of assessments for the Follow-up Period is presented in [Appendix 2](#).

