- h BICAMS will be assessed yearly. Since CVLT-II is not yet available in all the languages of the countries participating in this study, the patients will not be assessed with this portion of the BICAMS. The patients will only need to complete the other two components of the BICAMS test battery (Symbol Digit Modalities Test and Brief Visuospatial Memory Test Revised).

- i MRIs will be performed yearly
- j A structured telephone interview will be conducted by site personnel every 8 weeks ( $\pm$  3 days) to identify and collect information on any changes in the patient's health status that warrant an unscheduled visit (including new or worsening neurological symptoms) and possible events or infections. No telephone contact is needed in weeks where patient is performing on-site visits.

Patients who receive alternative MS therapies that may decrease B-cell levels will not be entered into the prolonged B-cell Monitoring period thereafter.

A dedicated (scheduled or unscheduled) follow-up visit directly prior to the start of an alternative MS treatment is required for patients who begin an alternative treatment for MS while in follow-up in order to assess the patient's clinical status and safety parameters (assessments to be performed as per schedule of assessments: follow-up or prolonged B-cell monitoring visits, depending on the study period in which the patient was in when the alternative treatment began).

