#### Pharmacodynamic effects

Within 4-6 hours after the first dose of fingolimod 0.5 mg, the lymphocyte count decreases to approximately 75% of baseline in peripheral blood. With continued daily dosing, the lymphocyte count continues to decrease over a two-week period, reaching a minimal count of approximately 500 cells/microlitre or approximately 30% of baseline. Eighteen percent of patients reached a minimal count below 200 cells/microlitre on at least one occasion. Low lymphocyte counts are maintained with chronic daily dosing. The majority of T and B lymphocytes regularly traffic through lymphoid organs and these are the cells mainly affected by fingolimod. Approximately 15-20% of T lymphocytes have an effector memory phenotype, cells that are important for peripheral immune surveillance. Since this lymphocyte subset typically does not traffic to lymphoid organs it is not affected by fingolimod. Peripheral lymphocyte count increases are evident within days of stopping fingolimod treatment and typically normal counts are reached within one to two months. Chronic fingolimod dosing leads to a mild decrease in the neutrophil count to approximately 80% of baseline. Monocytes are unaffected by fingolimod.

Fingolimod causes a transient reduction in heart rate and decrease in atrioventricular conduction at treatment initiation (see sections 4.4 and 4.8). The maximal decline in heart rate is seen within 6 hours post dose, with 70% of the negative chronotropic effect achieved on the first day. With continued administration heart rate returns to baseline within one month. The decrease in heart rate induced by fingolimod can be reversed by parenteral doses of atropine or isoprenaline. Inhaled salmeterol has also been shown to have a modest positive chronotropic effect. With initiation of fingolimod treatment there is an increase in atrial premature contractions, but there is no increased rate of atrial fibrillation/flutter or ventricular arrhythmias or ectopy. Fingolimod treatment is not associated with a decrease in cardiac output. Autonomic responses of the heart, including diurnal variation of heart rate and response to exercise are not affected by fingolimod treatment.

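### The protocol gives two different exceptions to prolonged B-cell monitoring after 96 weeks of follow-up, and they conflict for fingolimod and arguably for other lymphocyte-lowering drugs

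*Protocol*

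**What the plan says.** Prolonged B-cell monitoring starts after 96 weeks of follow-up. Three statements govern who enters it.

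- **General rule.** The opening of Protocol 3.1.4 says that any patient still depleted after the follow-up period "will continue to be monitored at 24-week intervals until the B-cell count has returned to the baseline value" or to the lower limit of normal, whichever is lower. It states no exception. Section 5.1.1.1, on delayed return of B cells, says the same in general terms.
- **Wording A, B-cell targeted therapy.** Protocol 3.1 says: "If the patients are receiving other B-cell targeted therapies, then the Follow-up Period will be stopped at 96 weeks regardless of their B-cell count". The synopsis and Appendix 2 footnote a agree. The text of 3.1.4 after Figure 4 gives the converse: "If further B-cell monitoring is required and the patient is not receiving any other B-cell targeted therapy, assessments will take place at clinical visits" and by telephone until repletion. SAP Appendices 1 and 3 carry copies of the synopsis text and the footnote.
- **Wording B, any B-cell-lowering MS therapy.** Further down in 3.1.4: "Patients who receive alternative MS therapies that may decrease B-cell levels will only be followed up for 96 weeks". The closing text of Appendix 2 has: "Patients who receive alternative MS therapies that may decrease B-cell levels will not be entered into the prolonged B-cell Monitoring period thereafter". SAP Appendix 3 copies this too.

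The only list of B-cell targeted drugs is in the exclusion criteria: "Previous treatment with B-cell targeted therapies (i.e., rituximab, ocrelizumab, atacicept, belimumab, or ofatumumab". No section names the MS therapies meant by Wording B, and none says which wording prevails.

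**The concern.** Both wordings are current text and stand together in 3.1.4 and in Appendix 2. They agree for a patient on a B-cell targeted drug and for a patient on no alternative therapy. They part for a drug that lowers B cells without being B-cell targeted.

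For such a patient, the sentence a site happens to follow settles whether 24-weekly visits and CD19 counts go on. It also settles the adverse event window, which 3.1.4 and 5.3.1 allow to run longer in patients who replete slowly. Protocol 3.2 defines the end of study by the last visit in B-cell monitoring, so that date is touched as well. On the analysis side, the listing in SAP 4.6.3 and the late CD19 repletion percentages in SAP 4.6.4.2 depend on who is kept under observation. If sites read the rule differently, late repletion data are selected by site and by subsequent therapy.

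**Working it through.** No planned figure is at issue, so the check is mainly a comparison of texts.

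**Step 1. Apply each wording to a patient still depleted at 96 weeks of follow-up.** The drug descriptions come from the seven product texts in Protocol Appendix 8.

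| Alternative therapy | What the protocol says of it | Wording A | Wording B |
|---|---|---|---|
| None | – | continues | continues |
| Drug on the B-cell targeted list, given for MS | named in the exclusion criteria | released | released |
| Natalizumab | circulating lymphocytes rise | continues | continues |
| Fingolimod | B lymphocytes named as affected | continues | released |
| Teriflunomide, dimethyl fumarate, Rebif | lower total lymphocytes or lymphopenia; B cells not named | continues | undefined |
| Plegridy, glatiramer | lower white cells or uncommon leukopenia; B cells not named | continues | undefined, weaker case |

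The fingolimod entry rests on its section 5.1: "The majority of T and B lymphocytes regularly traffic through lymphoid organs and these are the cells mainly affected by fingolimod". The conflict is therefore clear for one product text of seven. It is arguable for three more, and for further ones only if any fall in white cells is counted.

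**Step 2. Check whether such patients can exist.** Protocol 4.4.2 says that lymphocyte-depleting agents and lymphocyte-trafficking blockers should not be given while the patient is B-cell depleted. Section 5.1 of the fingolimod text describes it as blocking lymphocyte exit from lymph nodes, so the clearest example falls under that restriction. On the other hand, 3.1.4 foresees alternative MS treatment during follow-up, requires a visit just before it starts, and asks for follow-up to be completed regardless of it. The group is narrowed but not shown to be empty.

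**Step 3. Scale.** Inputs: last dose at Week 72, treatment period to Week 96, follow-up of 96 weeks (Protocol 3.1, 3.1.4); repletion time after the last infusion with median 72 weeks and range 27 to 175 in 51 Phase II patients (Protocol 5.1.1.1).

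- For completers, follow-up ends (96 − 72) + 96 = 120 weeks after the last planned infusion.
- Assume that repletion time is log-normal with median 72. Set σ from the range: σ = ln(175/72)/z = 0.888/z, or σ = ln(72/27)/z = 0.981/z.
- With z = 2.25 (approximate expected extreme of 51 values), σ = 0.39 to 0.44. With z = 2.07 (the 51/52 normal quantile), σ = 0.43 to 0.47.
- Share still depleted at 120 weeks = 1 − Φ(ln(120/72)/σ) = 1 − Φ(0.511/σ). This gives 0.10 to 0.12 for the first pair and 0.12 to 0.14 for the second, so about 10 to 14% overall.

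This is the share of completers in follow-up who would reach the point where the rule matters. It is not the share affected, which also requires being on a drug where the wordings differ. The documents give neither how many enter follow-up nor how many take such a drug.

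**The case against.** The strongest reply is that the wordings need not collide. The synopsis, 3.1 and footnote a say that B-cell targeted therapy stops follow-up at 96 weeks; they do not call it the sole exit. The continuing sentence in 3.1.4 applies only where further monitoring is required. A site reading all of 3.1.4 could treat Wording B as a second, specific exit and the opening sentence as a general rule qualified later. That reading is possible, but neither document states it, and Wording B still has no drug list.

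Three further replies stand in part:

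- The list of B-cell targeted drugs comes from an exclusion criterion on previous treatment, and nothing carries it formally into the follow-up rules. Fingolimod is nonetheless not among the drugs named anywhere as B-cell targeted.
- Section 4.4.2 restricts the clearest example, as shown above.
- The analysis harm is limited. CD19 and concomitant medication are collected at 24-weekly visits through the 96 weeks of follow-up under either wording (Protocol Appendix 2). Related serious adverse events are reported without time limit, and SAP 4.2 already counts patients who take any DMT after ocrelizumab.

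A reader might infer more than the documents support:

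- **That most alternative DMTs are affected.** Only fingolimod's text names B lymphocytes, and natalizumab's reports a rise in lymphocytes.
- **That one patient in four is affected.** The same assumption leaves about 23 to 27% depleted at 96 weeks after the last infusion. That would apply only if an early stopper's follow-up began on the day of the last infusion, whereas 3.1.4 starts it at the Early Treatment Discontinuation Visit. The figure is also not restricted to any drug.
- **That the rules cut short monitoring already under way.** They decide entry to prolonged monitoring, which begins after 96 weeks.

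**Conclusion.** The inconsistency is real and minor. The protocol states two different exceptions to prolonged B-cell monitoring, beside a general rule with none, and does not say how they relate. Taken literally, they give opposite instructions for a still-depleted patient on fingolimod. They leave the instruction undefined for other drugs that lower lymphocytes.

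The number affected is unknown. The 10 to 14% figure is context only. It rests on a log-normal shape, on a spread inferred from the extremes of 51 patients, and on those Phase II patients resembling the completers here. Patients who enter the extension study or switch to commercial ocrelizumab fall outside it. What is at stake is who stays in safety follow-up, how long adverse events are collected, and how complete the late repletion data are. The primary endpoint, the sample size and the efficacy inference are not affected.

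**What to change.** Reconcile the passages to a single trigger, and name the therapies it covers. The places are the protocol synopsis (description of study), 3.1, 3.1.4 (the opening rule and both later sentences), Appendix 2 (footnote a and closing text), and the copies in SAP Appendices 1 and 3. Check the result against the prohibited-therapy text in 4.4.2. Which trigger applies is for the sponsor's clinical team.

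In SAP 4.6.3, list every patient not repleted at the last available CD19 sample, with any alternative MS therapy and its start date. Patients released under either reading then stay visible.

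The cost is protocol wording and extra fields in a listing already planned. Depending on the trigger kept, there would be a few more 24-weekly visits or a few fewer patients under prolonged monitoring.

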### **3.1.5 Planned Total Sample Size**

This study will enroll approximately 750 patients. Please refer to the Section 6.1 for more details.

## **3.2 END OF STUDY AND LENGTH OF STUDY**

The end of the study treatment period has been defined as the date on which the last patient receiving the full study treatment reached the 96-week visit. Exception will be made for patients that have EDSS change at Week 96 and need confirmation of EDSS score after a further 24 weeks.

The end of the study is defined as the last patient last visit in the B-cell monitoring of the Follow-Up period. At the end of the study treatment, patients will be encouraged to be included in a separate LTE study to further evaluate the efficacy and safety of their DMT treatment, and this is independent of the DMT. This LTE will also aim to evaluate the relationship between the primary endpoint of this study and long-term outcome.

The total length of the study, from screening of the first patient to the end of the study, is expected to be approximately 5 years. This includes an enrollment period of approximately 12 months.

## **3.3 RATIONALE FOR STUDY DESIGN**

This is a Phase IIIb, prospective, multicenter, open-label, study to assess the efficacy and safety of ocrelizumab in patients with RRMS who have a suboptimal response to an adequate course of a DMT. The efficacy and safety of ocrelizumab has been studied in three randomized, double-blind, parallel group, controlled Phase III studies (WA21092 and WA21093 in relapsing MS and WA25046 in PPMS) with further follow-up ongoing in OLE phase. As there are limited data in patients who have switched to ocrelizumab after a suboptimal response to an adequate course of a DMT, a single-arm study is considered appropriate given the aims of this study. As the aim of the study is to evaluate the efficacy of ocrelizumab in this setting, the MRI results will be evaluated starting from week 8, as demonstrated in the Phase II clinical trial.

### **3.3.1 Rationale for Ocrelizumab Dose and Schedule**

The dose level of ocrelizumab administered in this study is 600 mg. The first dose will be administered as two 300-mg IV infusions in 250 mL 0.9% sodium chloride each separated by 14 days in order to lower the amount of ocrelizumab administered upon first exposure. The remaining doses will be administered as single 600-mg infusion in 500 mL 0.9% sodium chloride every 24 weeks to assess the tolerability of the intended administration regimen.

This dosing regimen is anticipated to be well-tolerated and is consistent with the dosing regimen used in Studies WA21092 and WA21093 in patients with RMS.

### **3.3.2 Rationale for Patient Population**

This study will be conducted in RRMS patients who show a suboptimal response to an adequate course of a DMT. RRMS is the most common type of MS, approximately 85% of MS patients present initially with RRMS (Confavreaux et al. 2000; Leray et al. 2015). Despite an adequate course of treatment with a DMT, a significant proportion of treated patients with RRMS will show signs of disease activity (Freedman 2014; Ziemssen et al. 2015; Tanasescu et al. 2015). Suboptimal responses are reported in approximately one-third of patients receiving DMT and therefore this population is considered to be appropriate to study the efficacy and safety of ocrelizumab.

